6.2.1.1 Permitted concomitant therapy requiring caution and/or action

Concomitant use of SARS-CoV-2 (COVID-19) vaccines is allowed among participants in this trial. There is no evidence to suggest that participants receiving either inclisiran/placebo or rosuvastatin are at increased risk for adverse events following a COVID-19 vaccination. However, since both inclisiran/placebo and COVID-19 vaccines are administered subcutaneously, it is recommended that the COVID-19 vaccine is administered +/- 7 days from inclisiran/placebo administration. Further, it is recommended that a different anatomical location is used for COVID-19 vaccine and inclisiran/placebo to help differentiate potential

local adverse reactions. Both COVID-19 vaccination administrations that occur prior to entering the study, and during the course of this study should be documented on the eCRF.

Rosuvastatin is a substrate of various transporter proteins (e.g. OATP1B1 and BCRP). The risk of myopathy (including rhabdomyolysis) is increased when rosuvastatin is administered concomitantly with certain medicinal products that may increase the plasma concentration of rosuvastatin due to interactions with these transporter proteins (e.g. ciclosporin and certain protease inhibitors including combinations of ritonavir with atazanavir, lopinavir, and/or tipranavir; please refer to local rosuvastatin SmPC for full details). Whenever possible, alternative medications should be considered, and, if necessary, consider temporarily discontinuing rosuvastatin therapy. In situations where co-administration of these medicinal products with rosuvastatin is unavoidable, the benefit and the risk of concurrent treatment and rosuvastatin dosing adjustments should be carefully considered.

Other co-medication increasing the incidence of myositis, myopathy or rhabdomyolysis including fibric acid derivatives, nicotinic acid, azole antifungals, protease inhibitors, macrolide antibiotics and ezetimibe should be used with caution.

The initiation of treatment or dosage up-titration of rosuvastatin in participants treated concomitantly with vitamin K antagonists (e.g. warfarin or another coumarin anticoagulant) may result in an increase in International Normalized Ratio (INR).

Oral contraceptive: Concomitant use of rosuvastatin and an oral contraceptive resulted in an increase in ethinyl estradiol and norgestrel. These increased plasma levels should be considered when selecting oral contraceptive doses.

Please always refer to the local rosuvastatin SmPC.

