6.2 Other treatment(s)

6.2.1 Concomitant therapy

LLT used by the participant in the 6 months prior to screening must be recorded on the appropriate eCRF pages.

All other medications, procedures, and significant non-drug therapies (including physical therapy and blood transfusions) used by the participant in the 3 months prior to screening must be recorded on the appropriate eCRF pages, independent of whether they will be continued during the study or not. Each concomitant drug must be individually assessed against all exclusion criteria.

Concomitant lipid-lowering therapy

In addition to the treatment with inclisiran/placebo and MTD of rosuvastatin, a participant's individual LLT has to be further escalated throughout the trial, if LDL-C is not at target. The participant's individual LLT should be complemented with ezetimibe (guideline recommendation Class I, Level B). If the LDL-C target is still not achieved, consider use of bile acid sequestrants (guideline recommendation Class IIb, Level C) ([Mach et al 2020](#)). Recently approved bempedoic acid may also be considered to be used, however, it is not depicted in the current guidelines and should thus be used secondarily after the aforementioned substances for further escalation of LLT. Concomitant PCSK9 mAb can be considered if a participant is deemed eligible by the Steering Committee. If the participant is deemed eligible for PCSK9 mAb treatment, then the blinded investigational treatment (inclisiran/placebo) will need to be discontinued. The Investigator's treatment decision as well as deviation from the above recommended LLT escalation need to be well documented on the appropriate eCRF pages. (See [Figure 3-2](#))

A new concomitant lipid-lowering drug must be assessed against all prohibited medications prior to its initiation.

Other concomitant therapy

All other medication, procedures, and significant non-drug therapies (including physical therapy and blood transfusions) administered after the participant was enrolled into the study must be recorded on the appropriate eCRF pages. A new concomitant drug must be assessed against all prohibited medications prior to its initiation.

If in doubt, the Investigator should contact the Novartis medical monitor before randomizing a participant or allowing a new medication to be started. If the participant is already enrolled, contact Novartis to determine if the participant should continue participation in the study.

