6.2.2 Prohibited medication

The simultaneous administration of the blinded investigational treatment, inclisiran/placebo, and PCSK9 mAb, CCI [REDACTED], is prohibited.

In case a PCSK9 mAb is planned to be administered, either based on the eligibility assessment by the Steering Committee or based on the investigator's decision to treat as per local standard of care, blinded investigational treatment (inclisiran/placebo), as outlined in [Section 3.4](#) and [Section 6.1.1](#) must be discontinued.

Table 6-3 Prohibited medication

Medication	Prohibition period	Action taken
Any investigational product	Full study duration	Discontinue all study treatment
Lomitapide	Full study duration	Discontinue all study treatment
Mipomersen	Full study duration	Discontinue all study treatment
Niacin	Full study duration	Discontinue all study treatment

Medication	Prohibition period	Action taken
Gemfibrozil	Full study duration	Discontinue all study treatment
Following medications are contraindicated to receive concomitantly with rosuvastatin		
• sofosbuvir/velpatasvir/voxilaprevir	Full study duration	Discontinue all study treatment
• ciclosporin	Full study duration	Discontinue all study treatment

Precautions and warnings:

Rosuvastatin must not be co-administered with systemic formulations of fusidic acid or within 7 days of stopping fusidic acid treatment. In patients where the use of systemic fusidic acid is considered essential, statin treatment should be discontinued throughout the duration of fusidic acid treatment. Rosuvastatin therapy may be re-introduced 7 days after the last fusidic acid. In exceptional circumstances, where prolonged systemic fusidic acid is needed, e.g. for the treatment of severe infections, the need for co-administration of rosuvastatin and fusidic acid should only be considered on a case by case basis and under close medical supervision.

The 40 mg dose of rosuvastatin is also contraindicated in patients with pre-disposing factors for myopathy/ rhabdomyolysis, including concomitant use of fibrates.

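### Protocol 6.2.1.1 puts nicotinic acid and fibric acid derivatives under caution and lets unavoidable ciclosporin use be weighed, while Table 6-3 prohibits niacin, gemfibrozil and ciclosporin and stops all study treatment

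*Protocol*

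**What the plan says.** Section 6.2.1.1 of the Protocol is headed as permitted concomitant therapy that needs caution or action. It handles two groups of drugs that bear on this point.

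- **Drugs that raise rosuvastatin levels through transporter proteins.** Ciclosporin is the first example named. The text begins with avoidance: "Whenever possible, alternative medications should be considered, and, if necessary, consider temporarily discontinuing rosuvastatin therapy". It then turns to use that cannot be avoided: "In situations where co-administration of these medicinal products with rosuvastatin is unavoidable, the benefit and the risk of concurrent treatment", together with rosuvastatin dose adjustment, is to be considered carefully.
- **Other co-medication that raises the incidence of muscle toxicity**, "including fibric acid derivatives, nicotinic acid, azole antifungals, protease inhibitors, macrolide antibiotics and ezetimibe should be used with caution".

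The section closes with "Please always refer to the local rosuvastatin SmPC". It does not mention Table 6-3.

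Table 6-3, in Section 6.2.2, lists niacin, gemfibrozil and ciclosporin as prohibited for the full study duration. The action for each is "Discontinue all study treatment". Ciclosporin stands under the sub-heading "Following medications are contraindicated to receive concomitantly with rosuvastatin".

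Other text bears on the same drugs. Section 6.2.1 says of lipid-lowering drugs: "A new concomitant lipid-lowering drug must be assessed against all prohibited medications prior to its initiation". It says of all other medication: "A new concomitant drug must be assessed against all prohibited medications prior to its initiation". It also sends doubts to the medical monitor. Section 9.1.1 lists use of prohibited treatment among the circumstances that require discontinuation. Section 5.2 excludes participants taking gemfibrozil (criterion 10) or ciclosporin (criterion 18) at screening or baseline.

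**The concern.** The two sections lead to different actions for the same drug. Under 6.2.1.1 a site may continue rosuvastatin with caution, adjust its dose, or pause it temporarily, and nothing is said about stopping inclisiran/placebo. Under Table 6-3 the drug is not allowed at all, and both rosuvastatin and inclisiran/placebo stop.

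The matter is one of participant safety. Section 6.2.1.1 itself links these drugs to myopathy or related muscle toxicity when given with rosuvastatin. A site that relied on that section alone could keep a participant on a combination that Table 6-3 forbids, including the contraindicated ciclosporin pair. Sites could also differ in whether they stop study treatment for the same event.

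**Working it through.** The conflict itself is a comparison of texts, so there is no plan figure to reproduce.

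**Step 1. The two instructions, drug by drug**

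| Drug | Section 6.2.1.1 | Table 6-3 | Named entry exclusion in 5.2 |
|---|---|---|---|
| Nicotinic acid (niacin) | Named; use with caution | Prohibited, full study; stop all study treatment | None |
| Gemfibrozil | Not named, but in the fibric acid class; use with caution | Prohibited, full study; stop all study treatment | Criterion 10 |
| Ciclosporin | Named as an example; avoid, or pause rosuvastatin, or weigh unavoidable use | Prohibited, full study, contraindicated with rosuvastatin; stop all study treatment | Criterion 18 |

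Two rows rest on standard nomenclature that the Protocol does not spell out: niacin and nicotinic acid are the same substance, and gemfibrozil is a fibric acid derivative.

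**Step 2. How direct each conflict is.** Nicotinic acid is the clearest case: it is named in both places with opposite instructions. Gemfibrozil is caught through its class. The caution is sensible for other fibrates, since Section 6.2.2 separately bars only the 40 mg rosuvastatin dose with concomitant fibrates, but gemfibrozil is not carved out. Ciclosporin is caught by the back-reference to the products just named as examples.

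**Step 3. Does other text settle it?** The checks in 6.2.1 and the rule in 9.1.1 lead a careful site to Table 6-3. The exclusions in 5.2 cover gemfibrozil and ciclosporin at entry, but not a start after randomization. None of this text says which instruction wins, and 6.2.1.1 has neither an exemption nor a cross-reference.

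**Step 4. How many participants a notice could still reach.** Inputs are from the Amendment 3 rationale: 1776 randomized, 1391 with treatment completed on 2 September 2024, last participant first treated on 26 February 2024.

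- Upper bound on participants still on treatment: 1776 − 1391 = 385. Anyone who had already stopped early lowers this figure.
- Last planned Day 360, counting first treatment as Day 1: 26 February 2024 + 359 days = 19 February 2025.
- Time from the Amendment 3 date to that day: 2 September 2024 to 19 February 2025 = 170 days.

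These figures describe the time and the number of participants open to correction. They are not an estimate of exposure to the three drugs, which the documents do not give.

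**The case against.** The strongest reply is that the plan already sets the order of events. Section 6.2.1.1 sits inside 6.2.1, whose checks against the prohibited list are worded as obligations, while 6.2.1.1 speaks only of what should be done or considered. On that reading the prohibition check comes first and the caution text applies only to drugs that pass it. Table 6-3 is in the very next section, 9.1.1 requires discontinuation, the medical monitor is available for doubts, and the SmPC reminder closes 6.2.1.1. For harm to follow, a site would have to miss all of these.

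Most of this stands, and it is why the point is small. It does not remove the conflict. A check that applies before a drug is started does not explain why a drug that must fail the check is also listed under caution, and a site that turns to the muscle-toxicity guidance finds nothing there to send it to the table.

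The objection is also right that ciclosporin is a weaker case than nicotinic acid. A reader might infer that the Protocol authorizes ciclosporin with rosuvastatin. It does not: no sentence says so, avoidance is put first, and ciclosporin appears only as an example within a wider group.

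**Conclusion.** The concern holds as a minor documentation conflict. Three drugs that Table 6-3 prohibits fall under softer instructions in 6.2.1.1, and the section does not say that the table prevails. The conclusion assumes the standard nomenclature noted above; the dates assume the planned schedule without visit delay.

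Stronger inferences are not supported.

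- A reader might infer that participants were exposed or harmed. The documents give no count, and the safeguards make exposure through this route unlikely.
- A reader might infer damage to the confirmatory muscle-related adverse event endpoint or to the handling of treatment discontinuation. Which instruction a site followed could change whether one participant counts as having discontinued, but no material effect can be shown and the planned analyses are unaffected.
- A reader might add the varying wording on intractable LDL-C and infer that only Section 4.1.1 lets rosuvastatin be stopped. Section 9.1.1 lists intractable cases under required discontinuation of inclisiran/placebo or rosuvastatin, so that inference fails. Aligning the wording is a sponsor policy choice and is not part of this point.

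**What to change.** Add one sentence to Section 6.2.1.1: *For any drug listed in Table 6-3, Table 6-3 prevails: the drug is prohibited and all study treatment must be discontinued if it is used.* This is better than deleting nicotinic acid and ciclosporin from the section, because deletion would leave gemfibrozil under the fibric acid caution, and that caution is still wanted for other fibrates.

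Send the clarification to sites while participants remain on treatment. After the last planned Day 360, use the concomitant-medication records to identify anyone who received one of the three drugs and to see what was done. The summary of prohibited medication in SAP Section 2.4.4 is by preferred term, so it gives counts but does not identify participants or show whether study treatment was stopped.

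The cost is one sentence, as a site clarification or in an amendment, plus a look through data already collected. Neither data collection nor the analysis changes.

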6.2.2 Prohibited medication

The simultaneous administration of the blinded investigational treatment, inclisiran/placebo, and PCSK9 mAb, CCI [REDACTED], is prohibited.

In case a PCSK9 mAb is planned to be administered, either based on the eligibility assessment by the Steering Committee or based on the investigator's decision to treat as per local standard of care, blinded investigational treatment (inclisiran/placebo), as outlined in [Section 3.4](#) and [Section 6.1.1](#) must be discontinued.

Table 6-3 Prohibited medication

Medication	Prohibition period	Action taken
Any investigational product	Full study duration	Discontinue all study treatment
Lomitapide	Full study duration	Discontinue all study treatment
Mipomersen	Full study duration	Discontinue all study treatment
Niacin	Full study duration	Discontinue all study treatment

Medication	Prohibition period	Action taken
Gemfibrozil	Full study duration	Discontinue all study treatment
Following medications are contraindicated to receive concomitantly with rosuvastatin		
• sofosbuvir/velpatasvir/voxilaprevir	Full study duration	Discontinue all study treatment
• ciclosporin	Full study duration	Discontinue all study treatment

Precautions and warnings:

Rosuvastatin must not be co-administered with systemic formulations of fusidic acid or within 7 days of stopping fusidic acid treatment. In patients where the use of systemic fusidic acid is considered essential, statin treatment should be discontinued throughout the duration of fusidic acid treatment. Rosuvastatin therapy may be re-introduced 7 days after the last fusidic acid. In exceptional circumstances, where prolonged systemic fusidic acid is needed, e.g. for the treatment of severe infections, the need for co-administration of rosuvastatin and fusidic acid should only be considered on a case by case basis and under close medical supervision.

The 40 mg dose of rosuvastatin is also contraindicated in patients with pre-disposing factors for myopathy/ rhabdomyolysis, including concomitant use of fibrates.

6.2.3 Rescue medication

Not applicable for the blinded investigational treatment, inclisiran/placebo. For the open label study treatment, rosuvastatin, please always refer to the local SmPC.

6.3 Preparation and dispensation

Blinded investigational treatment, inclisiran/placebo:

- Each study site will be supplied with study drug in packaging as described in [Section 6.1.1](#).
- A unique medication number is printed on the study medication label.
- Investigator staff will identify the study medication kits to dispense to the participant by contacting the IRT and obtaining the medication number(s). Study medication (inclisiran/placebo) accountability and reconciliation data are recorded in the IRT system. The study medication has a 2-part label (base plus tear-off label), immediately before dispensing the medication kit to the participant, site personnel will detach the outer part of the label from the packaging and affix it to the source document

Open label study treatment rosuvastatin:

- Commercially available rosuvastatin will be sourced locally and supported by the sponsor.

6.3.1 Handling of study treatment and other treatment

6.3.1.1 Handling of study treatment

Blinded investigational treatment, inclisiran/placebo, must be received by a designated person at the study site, handled, stored and kept safely and properly in a secured location to which only the investigator and the designated site personnel have access. Upon receipt, all study treatment must be stored according to the instructions specified on the labels.

For open label study treatment, rosuvastatin, the above is also applicable when stored at the site. In case rosuvastatin is supplied by another facility, e. g. local pharmacy, it needs to be ensured all processes regarding the proper handling of the open label study medication are followed.

Clinical supplies are to be dispensed only in accordance with the protocol. Technical complaints are to be reported to the respective Novartis Country Organization Quality Assurance.

Medication labels will be written in the local language and will comply with the legal requirements of each country. Label information will include the storage study treatment conditions. No information about the participant except for the medication number will be disclosed.

For open label study treatment, rosuvastatin, that is administered at home, participants will be asked to -bring all used/unused study treatment and its packaging at each study visit.

The investigator must maintain an accurate record of the shipment and dispensing of all study treatment (including open label study treatment, rosuvastatin) in a drug accountability log. Monitoring of the drug accountability of both of the study treatments, blinded inclisiran/placebo and open label rosuvastatin, will be performed by field monitors during site or remote visits, and at the completion of the trial, as described in the Monitoring Plan.

The site may destroy and document the destruction of unused study treatment, drug labels and packaging as appropriate in compliance with site processes, monitoring processes, and per local regulation/guidelines. Otherwise, the investigator will return all unused blinded investigational treatment, packaging, drug labels, and a copy of the completed drug accountability log to the Novartis monitor or to the Novartis address provided in the investigator folder at each site.

6.3.1.2 Handling of other treatment

The following non-study treatments have to be monitored specifically, as described in the Monitoring Plan:

- All lipid-lowering therapies

6.3.2 Instructions for prescribing and taking study treatment

Blinded investigational treatment, inclisiran/placebo, will not be dispensed to the participants. Study drug injections will be performed exclusively at the study site by qualified clinical study site staff under the supervision of the investigator or designee.

The preferred site of injection is the abdomen. Alternative injection sites include the upper arm or thigh. Injections should not be done into areas of active skin disease or injury such as sunburns, skin rashes, inflammation, tattoos or skin infections.

Participants will be administered one subcutaneous injection of blinded investigational treatment, inclisiran/placebo, at pre-defined visits, as specified in the Schedule Visit (Table 8-1).

Injections will be administered after all other study assessments have been completed for the visit.

Blinded investigational treatment, inclisiran/placebo, assigned by the IRT will be recorded in the IRT system. All injections to the participant as well as study drug interruptions/discontinuations (i.e. no injection at a designated dosing visit) during the study must be recorded on an appropriate eCRF and within IRT.

Open label study treatment, rosuvastatin, will be commercially sourced locally. Rosuvastatin should be taken by the participant at a certain dose level and time of day as instructed by the investigator and according to the local SmPC. Drug reconciliation of open label study treatment, rosuvastatin, needs to be performed and documented to capture the dispensing and daily intake of rosuvastatin on participant level. Rosuvastatin dispensing or accountability will not be captured within IRT. For this reason, it is important that any drug interruptions, or discontinuations for rosuvastatin during the study be recorded in the eCRF.

6.4 Participant numbering, treatment assignment, randomization

6.4.1 Participant numbering

Each participant is identified in the study by a Participant Number (Participant No.), that is assigned when the participant is enrolled for screening and is retained for the participant throughout his/her participation in the trial. A new Participant No. will be assigned at every subsequent enrollment if the participant is re-screened. The Participant No. consists of the Center Number (Center No.) (as assigned by Novartis to the investigative site) with a sequential participant number suffixed to it, so that each participant's participation is numbered uniquely across the entire database. Upon signing the ICF, the participant is assigned to the next sequential Participant No. available.

